1.2 Rationale

Across every stage of the HIV care continuum, YBLMT underperform compared to their White peers.²⁻⁴ Among interventions for Black or Latino sexual and gender minorities,²⁶⁻⁴⁶ few focus on intersectional stigma as a key intervention target.^{30,38,41-46} Stigma-reduction interventions are primarily delivered in-person, focus on older ages, or include either HIV-positive or HIV-negative MSM. HealthMpowerment (HMP Original; R01MH093275) was designed to engage HIV-positive, negative, and status-unknown YBLMT and to reduce sexual risk via a mobile optimized online platform.⁴⁷ This approach helped remove logistical, financial, and stigma barriers to intervention participation; however, engagement as measured by detailed data collected as users interact with mHealth interventions (i.e. paradata) varied greatly between participants.⁴⁸ Through a R21 study (MH105292), we explored whether participants in the HMP intervention arm reported reductions in HIV-related stigma outcomes. Using behavioral data and intervention paradata, our mixed-methods results suggest that participants' user-generated content (e.g., discussions in HMP's diverse forums) regarding intersectional stigma was associated with improved psychological well-being and HIV care outcomes.⁴⁹⁻⁵¹

A gap in knowledge exists regarding how participants' engagement with mHealth interventions is linked to HIV prevention and care outcomes. Paradata can provide purposeful process metrics (e.g., timestamps in system logs to quantify time spent using the intervention, types of features used) to assess intervention engagement. We will use paradata to gauge how intersectional stigma and HIV care continuum outcomes differ based on participants' frequency (exposure), time spent (engagement), and types of intervention components participants used (usage) in the app. We will also use paradata to characterize YBLMT's discussions with each other within HMP Stigma social networks, and study how these exchanges influence intervention engagement and HIV care continuum outcomes over time.

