3.1 Study Population

We will enroll 1,050 YBLMT from across the United States into this 3-arm randomized trial. Participants' self-reported HIV status at baseline will be used for allocation in our HIV-status stratified randomization procedure.

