4.0 SELECTION AND ENROLLMENT OF STUDY PARTICIPANTS

4.1 Inclusion Criteria (All study arms)

- Aged 15-29 years (inclusive) at time of screening
- Identify as Black/African American and/or Latino/Hispanic
- Current U.S. resident (verified by zip code)
- Speak and read English
- Report anal intercourse in the past 6 months
- Assigned male sex at birth (no restrictions on current gender identity)
- Has a smartphone
- If HIV-positive, does not report a hemophilia diagnosis or current use of anti-coagulation medication

Additional Inclusion Criteria (Referred Peers from Peer-Referral Arm)

- Invited by current participant in Intervention Arm 2 (approximately 300 participants)
- Any race/ethnicity

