5.0 STUDY PROCEDURES

5.1 Enrollment Procedures

We will enroll a total of 750 participants. Of these participants, 300 will be HIV-negative and 450 will be HIV-positive. After participants are consented, participants will complete a baseline CASI survey and then will be randomized into the Tailored Information-Only Control (Attention Control), Researcher-Created HMP Network (Intervention Arm 1), or HMP with Peer-Referral Network (Intervention Arm 2). Intervention Arm 2 will only have 150 HIV-positive participants randomized to it, as the remaining participants will be peers who are referred by their peers and enroll if eligible. Upon enrollment, all participants will be provided a link to access the HMP app through the Apple App Store or the Google Play Store for Android. Once downloaded, participants will create their app account by entering their email address, creating a username, password, and PIN, entering their mailing address, opting in or out of notifications, and selecting an avatar.

Those randomized in the Tailored Information-Only Control (Attention Control) will be given a streamlined version of the app. They will have access to the Care Locator and Knowledge Center articles and be able to message the Care Navigator. HIV-negative and sero-unknown participants will be able to request HIV home test kits. HIV-positive participants will be sent HemaSpot devices at Baseline, 6 months, and 12 months. They will not have access to the interactive forums, activities, or the Ask and Expert feature.

Those randomized in the Researcher-Created HMP Network (Intervention Arm 1) will have access to the full HMP app, including access to the Arm 1 Forum in which participants will be able to create threads and comment on any threads in the forum, whether moderator- or usergenerated.

Those randomized to the Peer-Referral Network (Intervention Arm 2) will have access to the full HMP app, including access to the Arm 2 Forum in which participants will be able to create threads and comment on any threads in the forum, whether moderator- or user-generated. The only difference between this version and the Intervention Arm 1, is that two thirds of the users (300) that comprise this group are added by peer referral by the 150 participants who were randomized into this arm.

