5.4 Intervention/Investigation Procedures

5.4.1. Randomized Trial Design

We will test whether a smartphone application (app) intervention (HMP Stigma) that promotes user-generated content and engagement to address intersectional stigma is associated with *successful engagement in care* as compared to an information-only control arm consisting of online informational articles and resources curated for YBLMT (Specific Aim 1). We will then examine how user engagement mediates the changes observed in stigma and HIV care outcomes across the 12-month follow-up period (Specific Aim 2). To describe how the social network composition of HMP Stigma affects user engagement and our HIV prevention and care outcomes across a 12-month follow-up period (Specific Aim 3), we will allow the composition of the intervention networks to vary. Participants randomized to Intervention Arm 1 will engage in a researcher-created network where half of the participants are HIV-positive. Participants randomized to Intervention Arm 2 will engage in a peer-referred network in which they may invite 2 peers (irrespective of race/ethnicity and/or HIV status) into the study. All participants who are randomized into Arm 2 will be HIV positive and we assume that peers they refer will be a mix of HIV-negative, HIV-positive, and HIV-unknown status.

5.4.2 HemaSpot Package, Delivery and Tracking: 120

At baseline and months 6 and 12, HIV-positive participants will be mailed a HemaSpot package which contains: 1) one HemaSpot kit with all necessary materials to perform a finger prick, a biohazard bag, and study labels; 2) an instructional booklet for how to properly collect a specimen for the HemaSpot device; 3) a return envelope addressed to the processing lab with pre-paid postage; and 4) a lab sheet which includes the participant's study ID. The U. Penn team will

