10.2 Power Estimates

The primary outcome for the proposed trial is stratified by HIV status and defined as *successful* engagement in care. For HIV-positive participants at baseline, we define successful engagement in HIV care as consistent VS across the 12-month trial (per IOM guidelines²¹⁸). For HIV-negative

or sero-unknown at baseline, we define successful engagement in care as participation in routine HIV testing (2 HIV tests with at least 3 months apart from one another, per CDC guidelines²¹⁹). We define power as correctly identifying the difference in the proportions of YBLMT with serospecific engagement in HIV care within 12 months of each intervention arm (2 arms: HMP Stigma with researcher-created network, HMP Stigma with peer-referred network) to the control arm (Information Control), thus powering for 3 independent hypothesis tests. Our sample size calculations are based on pair-wise HIV-stratified comparisons of the 3 groups in terms of proportion of successful engagement using a two-sided significance level of 0.05 altered by the number of comparisons using a Bonferroni adjustment (significance level is 0.017 for 3 comparisons). To have 80% power to detect a minimum effect size (OR=1.9) of successful engagement in care between the 3-arm trial, we will require at least 450 HIV-negative and 450 HIV-positive participants to detect a 17% difference in successful engagement in. In the event of a 20% loss to follow-up, we will have sufficient power to detect an OR=2.1 (18% difference) at alpha=.017. Participants may continue the study even if they miss an assessment intermittently. We will compare those who completed different follow-up interviews with those who did not on key baseline predictors to check for possible sampling bias. Our analysis will use ITT as appropriate.

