10.3 Statistical Analysis Plan

10.3.1 Specific Aim 1:

Specific Aim 1 is to test whether a smartphone application (app) intervention (HMP Stigma) that promotes user-generated content and engagement to address intersectional stigma is associated with successful engagement in care as compared to an information-only control arm consisting of online informational articles and resources curated for YBLMT. Clinical and demographic characteristics will be described for the entire sample, and by treatment group. These will be compared between treatment groups using ANOVA or Kruskal-Wallis test for continuous variables, and chi-square tests for categorical variables. We will conduct primary analyses of our successful engagement in care outcome using logistic regression analyses to compare each active treatment group to the control in pairwise comparison tests at an adjusted significance level of 0.017 to reduce Type-I errors in our 3-arm trial. This approach allows us to also test for differential efficacy between the two intervention conditions (i.e., Does peer-referral HMP outperform the researcher-created HMP arm?).

Logistic regression analyses will be stratified by serostatus. The regression will be run with group assignment only in the model. Among HIV-positive participants, we will examine how intervention conditions influence YBLMT's likelihood of consistent VS over 12 months. We will also test intervention effects on retention in care per IOM guidelines (i.e., proportion of HIV-positive participants who obtain at least 2 viral load tests (at least 3 months apart) within 12 months). For HIV-negative YBLMT, we will compare the proportion of participants who obtain at least 2 HIV tests (at least 3 months apart) within 12 months across arms. Estimates will be calculated and presented with corresponding 95% exact binomial confidence intervals. In secondary outcome analyses, we will compare arms across other HIV care continuum outcomes, as well as stigmarelated (e.g., reduction in HIV-related stigma) outcomes, using a logistic regression with group assignment on the model assuming no imbalances due to successful randomization.

10.3.2 Specific Aim 2:

Specific Aim 2 is to explore whether user engagement, as measured by paradata, mediates the intervention effects observed in stigma and HIV care outcomes.

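### The Aim 1 comparisons are framed on young Black or Latino participants, but Arm 2 alone admits referred peers of any race/ethnicity and the plan does not say whether they count; this bears mainly on the HIV-negative stratum

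*Combined protocol and SAP*

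**What the plan says.** **Population in the analysis text.** Section 10.2 defines power on the "difference in the proportions of YBLMT with serospecific engagement in HIV care within 12 months". Section 10.3.1 uses the same label: "For HIV-negative YBLMT, we will compare the proportion of participants who obtain at least 2 HIV tests". Section 3.1 applies it to the whole sample: "We will enroll 1,050 YBLMT from across the United States into this 3-arm randomized trial".

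**Eligibility.** Section 4.1 requires participants in all arms to "Identify as Black/African American and/or Latino/Hispanic", then lists "Any race/ethnicity" among the additional criteria for referred peers. Section 5.4.1 confirms that the waiver is intended: Arm 2 participants are told that "they may invite 2 peers (irrespective of race/ethnicity and/or HIV status) into the study".

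**Who is in Arm 2.** Section 5.1 says that "two thirds of the users (300) that comprise this group are added by peer referral by the 150 participants" randomised to it, and that those 150 are all HIV-positive. Section 5.3 says that referred peers are not randomised. Section 3.2 assumes that half of the peers will be HIV-negative or of unknown status.

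**Model.** Section 10.3.1 runs the primary logistic regression separately by serostatus, with study arm as the only term. Baseline characteristics are to be compared across arms, but no action follows from that comparison.

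**The concern.** Two descriptions of the Aim 1 population sit side by side, and no section says which one governs. Two analysts following the text could therefore analyse different people in Arm 2.

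If every enrolled peer counts, Arm 2 is drawn from a wider eligible population than Control and Arm 1. A difference between arms could then partly reflect who was eligible rather than the app, and it would not be a result about YBLMT. If only YBLMT count, the Arm 2 number behind the HIV-negative sample size in section 10.2 is no longer assured.

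The HIV-negative/unknown stratum carries the weight. No HIV-negative participant is randomised to Arm 2, so that cell consists entirely of people recruited under the relaxed criterion.

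**Working it through.** **1. Where the 450 HIV-negative participants come from.** Sections 3.2 and 5.1 give 150 in Control and 150 in Arm 1. Arm 2 supplies half of 300 peers: 0.5 × 300 = 150. The total is 150 + 150 + 150 = 450, the number in section 10.2. It is reached only if every expected HIV-negative peer counts. The 450 HIV-positive participants are the 3 × 150 randomised and need no peers. Total enrolment is 750 randomised + 300 peers = 1,050, so the 1,050 in section 3.1 are neither all randomised nor necessarily all YBLMT.

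**2. The plan's own power figure.** Section 10.2 states 80% power for an odds ratio of 1.9, or 17 points, with 450 per stratum (150 per arm) at two-sided 0.017. This does not reproduce. The largest difference an odds ratio of 1.9 allows is (√1.9 − 1)/(√1.9 + 1) = 15.9 points. The best power for that odds ratio at 150 per arm is 64.6%; at an unadjusted 0.05 it is 79.0%. That is a separate matter, and only the change in power from this baseline is used here.

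**3. Assumptions.** The documents do not give the share w of HIV-negative peers who are not Black or Latino, the gap g in their success rate over YBLMT, or the control rate. I take w = 10-50%, g = +10 to +20 points and Control 42%. The sign of g is also an assumption.

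**4. All peers counted, no app effect.** The Arm 2 success rate is 0.42 + w × g. With d = w × g, n = 150 per arm and critical value c = 2.387 (two-sided 0.017):

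P(reject) = Φ((d − c·SE0)/SE1) + Φ((−d − c·SE0)/SE1),

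where SE0 is the pooled and SE1 the unpooled standard error. For w = 50% and g = 20: d = 0.10, SE0 = 0.0576, SE1 = 0.0573, giving 0.256.

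| w | g (points) | Spurious difference (points) | P(reject), nominal 0.017 |
|---|---|---|---|
| 10% | 10 | 1.0 | 0.019 |
| 25% | 15 | 3.75 | 0.043 |
| 50% | 10 | 5.0 | 0.065 |
| 50% | 20 | 10.0 | 0.256 |

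A control rate of 50% gives nearly the same values (0.019, 0.042, 0.065, 0.258).

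**5. Only Black or Latino peers counted.** The Arm 2 cell is 150 × (1 − w), against 150 in Control. Power = Φ((0.16 − c·SE0)/SE1) for 42% v 58% (odds ratio 1.9):

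| w | Arm 2 n | Power | Loss (points) |
|---|---|---|---|
| 0 | 150 | 65.2% | – |
| 10% | 135 | 62.4% | 2.8 |
| 25% | 112 | 57.1% | 8.1 |
| 40% | 90 | 50.6% | 14.6 |
| 50% | 75 | 45.1% | 20.1 |

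For a 17-point difference (41.5% v 58.5%), power falls from 71% to 69%, 64% and 51% at w = 10%, 25% and 50%, a similar loss.

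**6. HIV-positive stratum.** The 150 randomised Arm 2 members meet the planned number without any peers. If about 150 HIV-positive peers were pooled with them, the spurious difference would be 0.5 × w × g, or 0.5 to 5 points on the same assumptions. The documents do not say whether they would be pooled.

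**The case against.** **YBLMT may be loose shorthand.** Section 2.1 and the opening of section 10.2 define the outcome on HIV-positive and HIV-negative participants; the YBLMT sentence in 10.2 defines power. Sections 5.4.2 and 8.2 use YBLMT where they plainly mean participants, and the abstract describes the 1,050 as racially and ethnically diverse. This stands in part: the endpoint itself is not tied to race/ethnicity. But section 10.3.1 names YBLMT for the comparison, and reading it as shorthand settles the question by counting everyone, which is the case of unequal eligibility.

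**A tempting stronger reading is that the protocol itself expects these peers to do better**, so that Arm 2 is biased towards the sponsor's hypothesis. Section 1.2 does say: "Across every stage of the HIV care continuum, YBLMT underperform compared to their White peers". That compares YBLMT with White peers only, gives no figure, and predicts nothing about referred peers, who may be mostly Black or Latino or may belong to other groups. The direction of bias is therefore not in the documents.

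**Another is that Arm 2 as a whole is measured on a different population.** Peers are two thirds of the arm, but the HIV-positive comparison can rest on randomised participants alone.

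**Non-randomisation is the larger problem.** Race/ethnicity is one of many ways in which referred peers may differ, and restricting on it leaves the HIV-negative Arm 2 comparison non-randomised. This stands in full, and the fix has to say so. It does not remove the need to define the population.

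**Conclusion.** The point holds as an undefined analysis population with unequal eligibility between arms, chiefly in the HIV-negative/unknown stratum. It should be corrected before analysis. Without a stated rule, either Arm 2 is compared across different eligible populations, or the 450 HIV-negative participants in section 10.2 are not reached (unless all 150 expected peers happen to be Black or Latino).

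The size is conditional. Under the assumed shares, gaps and 42% control rate, counting all peers moves the false-positive rate from a nominal 0.017 to between 0.019, which is negligible, and 0.26, which needs half the peers to be neither Black nor Latino and a 20-point gap. Excluding them costs about 3 to 20 points of power. The count in step 1 needs no assumption beyond the plan's own half-and-half split.

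**What to change.** - **Sections 10.2 and 10.3.1:** state that primary Aim 1 comparisons involving Arm 2 use participants who meet the all-arms race/ethnicity criterion, or adjust for race/ethnicity. Control and Arm 1 contain nobody outside that criterion, so a term for meeting it gives the same arm contrast as restriction and recovers no power. Show the all-peers result as a sensitivity analysis and keep all peers for Aim 3.
- **HIV-positive stratum:** base the Arm 2 comparison on the 150 randomised participants.
- **HIV-negative stratum:** label the Arm 2 comparison as non-randomised wherever it is reported.
- **Data:** confirm that race/ethnicity is recorded for referred peers, since it is not an eligibility criterion for them.
- **Section 3.1:** replace the description of 1,050 randomised YBLMT with 750 randomised YBLMT plus up to 300 non-randomised peers of any race/ethnicity.
- **Section 10.2:** restate the HIV-negative Arm 2 size and power counting only YBLMT peers, with the assumed share given.

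The cost is protocol and SAP wording, plus one data check. Open peer referral is unchanged. The downside is a smaller analysed Arm 2 and lower stated power.

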3.3.2 Intervention and control arms

Participants in all arms will have access to a Care Navigator through the intervention or control app. The Care Navigator will utilize existing online databases of resources (e.g. AIDSVu.org Locators, CDC's GetTested.cdc.gov locators, POZ.com's Service directory) to connect participants to trusted HIV testing and care services in their communities as needed. The Care Navigator will also monitor the Forums to identify additional HIV knowledge needs and manage the Ask an Expert provider Q&A to triage medical questions to one of two board-certified HIV care providers. During all study years the Care Navigator will work closely with the YAB to elicit service-related needs and concerns among YBLMT that can be integrated into HMP Stigma.

Control Arm: The HMP Stigma Information-Only Control Arm will feature a streamlined version of the app that provides curated information and other content for YBLMT. This content will follow the design of HMP Original where control arm participants had access to HIV-related Knowledge Center articles of the main intervention without access to the engagement features such as the interactive forums or doctor Q&A. HIV-negative and sero-unknown participants will also be able to request HIV home test kits. Our choice of control arm balances equipoise with research study design; in HMP Original, control arm participants also experienced a statistically significant intervention benefit.⁴⁷ We have taken this effect into account in our sample size calculations.

HMP Stigma: We have used the Stigma Framework¹²⁸ alongside our findings from HMP Original to guide the design of our proposed intervention features and content (Table 1) and study measures (Table 2). Eligible, enrolled participants who are randomized to intervention Arms 1 (researcher-created network) and 2 (peer-referred networks) will have access to all the features of HMP Stigma. These features include forums where users can start or participate in threads, a knowledge center filled with short articles on a range of topics that can be added and commented on, a provider platform where health questions can be submitted to be answered by a health care provider, a user profile where users can personalize and update their information, and finally, an ordering platform where users can order and track testing kits.

Table 1: HMP Stigma Core Intervention Components and Scientific Rationale						

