8.0 PARTICIPANT MANAGEMENT

8.1 Tracking Participants / Follow-up

A detailed retention plan (see "HMP SOP-Recruitment and Retention.docx") will draw on our prior successful protocols with hard to reach populations to achieve ≥80% retention rate for the 3month assessment.⁴⁷ In our experience, successful retention has several key elements. First, it is critical to obtain accurate follow-up contact information. We will use best practices to retain participants while being sensitive to undue disclosure of YBLMT participating in the study. One barrier to retention among youth is changing cell phone numbers. Study staff will include a reminder for participants in the 3-, 6-, and 9-month survey emails to update their email and SMS contact information if it has changed in the past 3 months. Every effort will be made to reduce attrition as retention is critical to our study efforts. In the event that participants do not respond complete a follow-up survey within 7 days of the first email and in-app request, they will receive a second email with the link and an in-app notification. A third attempt will be made before the study coordinator or Care Navigator calls participants. Correlates of missing data and attrition will be carefully examined. Participants who miss one or more follow-up assessments may still continue in the study. We will compare those who completed different follow-up interviews with those who did not on key predictors from the baseline assessment to check for possible sample bias. The use of the Expectation-Maximization algorithm in the longitudinal analyses will also aid to overcome missing data concerns when appropriate. 192,193

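### Section 10.2 claims 80% power for OR 1.9, but 150 per arm at alpha 0.017 gives at most about 65%, and OR 1.9 cannot produce a 17-point difference

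*Combined protocol and SAP*

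**What the plan says.** Section 10.2 bases the sample size on "pair-wise HIV-stratified comparisons of the 3 groups", with a "two-sided significance level of 0.05 altered by the number of comparisons using a Bonferroni adjustment (significance level is 0.017 for 3 comparisons"). The claim is "To have 80% power to detect a minimum effect size (OR=1.9) of successful engagement in care between the 3-arm trial", and for this "we will require at least 450 HIV-negative and 450 HIV-positive participants to detect a 17% difference in successful engagement in" care. For 20% loss to follow-up it adds that "we will have sufficient power to detect an OR=2.1 (18% difference) at alpha=.017".

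Section 3.2 gives 150 per arm in the HIV-positive stratum. In the HIV-negative or unknown stratum it gives 150 each in control and Arm 1, and Arm 2 is expected to receive about 150 referred peers. Section 10.3.1 analyses the primary outcome by pairwise logistic regression at 0.017, with treatment group as the only term.

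Neither section gives a control-arm success rate. Section 3.3.2 refers to the benefit seen in the control arm of the earlier trial and says "We have taken this effect into account in our sample size calculations".

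**The concern.** The odds ratio, the absolute difference, the alpha, the power and the sample size are all stated, so each can be checked against the others. An odds ratio of 1.9 looks too small to correspond to 17 points at any control rate, and 150 per arm looks too few for 80% power at a Bonferroni-adjusted alpha.

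These are the only power figures for the primary outcome. If they are too favourable, a non-significant result invites the reading that an effect of OR 1.9 would probably have been found. Section 5.4.6 also asks the DSMB to watch for dropout that threatens credible results, and 10.2 tells it that 20% loss leaves adequate power for OR 2.1.

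**Working it through.** **Inputs.** Two-sided alpha 0.017, so z = 2.387; 80% power, so z = 0.842; OR 1.9 or 17 points; 150 per arm; fallback OR 2.1 or 18 points with 150 × 0.8 = 120 per arm (all from 10.2 and 3.2). There is no covariate adjustment (10.3.1). The control rate is not given, so power was maximised over all control rates. The ceilings below therefore need no assumption about it.

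**Step 1: can OR 1.9 be a 17-point difference?** For a given odds ratio k the difference is largest when the two rates are symmetric about 50%, with control rate 1/(1+√k). The maximum is (√k − 1)/(√k + 1).
- k = 1.9: √k = 1.378, so 0.378/2.378 = 15.9 points (42.0% against 58.0%).
- k = 2.1: √k = 1.449, so 0.449/2.449 = 18.3 points. The pairing of OR 2.1 with 18 points is possible.
- Smallest odds ratio for a difference d: ((1+d)/(1−d))². For d = 0.17 this is (1.17/0.83)² = 1.99.

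**Step 2: power for OR 1.9, 150 against 150.** Power = Φ{[d − z·√(2p̄(1−p̄)/n)] / √[(p₁q₁ + p₂q₂)/n]}. At the best control rate, p₁ = 0.420, p₂ = 0.580, p̄ = 0.5 and p₁q₁ + p₂q₂ = 0.487:
- Numerator: 0.1591 − 2.387 × √(0.5/150) = 0.1591 − 0.1378 = 0.0213.
- Denominator: √(0.487/150) = 0.0570.
- Φ(0.374) = 64.6%.

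The stated 80% is not reproduced. A Wald calculation gives 64.0%, arcsine 64.8%, and simulation at the best control rate 65.4%.

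**Step 3: sample size for 80% power at OR 1.9.** n = (2.387 × 0.7071 + 0.842 × 0.6981)² / 0.1591² = 2.275² / 0.0253 = 204.5, so 205 per arm or 615 per stratum.

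**Step 4: the 20%-loss figure, OR 2.1, 120 against 120.** At the best control rate (41%): 0.1834 − 2.387 × √(0.5/120) = 0.0293; divided by 0.0635 this is 0.462; Φ = 67.8%. With no loss (150 per arm), OR 2.1 reaches at most 78.9%.

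**Step 5: dependence on the control rate (alpha 0.017).**

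| Control rate | OR 1.9, 150/arm | OR 2.1, 120/arm | 17 points, 150/arm (implied OR) |
|---|---|---|---|
| 20% | 51% | 55% | 81% (2.35) |
| 30% | 61% | 65% | 74% (2.07) |
| 40% | 64% | 68% | 71% (1.99) |
| 50% | 63% | 66% | 73% (2.03) |
| 60% | 58% | 60% | 79% (2.23) |
| 70% | 48% | 50% | 89% (2.87) |

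**Step 6: what would reproduce the stated figures?** At unadjusted two-sided 0.05, the two scenarios give at most 79.0% (OR 1.9, 150 per arm) and 81.5% (OR 2.1, 120 per arm). A 2:1 comparison at 0.017 gives 79.1% (300 against 150) and 82.0% (240 against 120). Either could be the origin; the document does not say.

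**Step 7: effect detectable with 80% power at 0.017, rates symmetric about 50%.** OR 2.12 (18.6 points) at 150 per arm; OR 2.32 (20.7 points) at 120 per arm. If OR 1.9 is kept, power after 20% loss is at most 53%.

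**The case against.** The strongest reply is that the 17-point difference, not the odds ratio, was the design target. Power for 17 points with 150 per arm is never below about 71%, and it reaches 80% when the control rate is about 21% or lower, or about 62% or higher. This is correct, and it is a good reason to require the control rate. It does not save the text: in those ranges 17 points corresponds to an odds ratio of about 2.29 or more, so 1.9 cannot be the minimum detectable effect. Without the control rate, the document does not show which of the two figures is the slip.

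A second reply is that HIV-positive referred peers could bring Arm 2 to about 300 in that stratum, giving 79.1% for OR 1.9 against 150 controls. That covers one comparison only, relies on non-randomised peers who stay clustered with their referrer, and departs from the 450 per stratum on which 10.2 rests. Arm 1 against control, and the planned HIV-negative comparisons, remain at 150 against 150.

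Rounding helps little: OR 1.95 has at most 68.6% power. Reading 17% as a relative difference would fit OR 1.9 at 69% against 81%, but power there is only about half, and 10.2 speaks of a difference in proportions.

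Two further points are fair. The analysis, alpha and endpoint are unaffected, so this is a misstated design claim and not a source of bias. And although the only numerical target in the protocol is a "retention rate for the 3month assessment" of at least 80%, section 8.1 defers to a separate retention SOP that may set a 12-month one.

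**Conclusion.** The concern holds. For the pairwise test that the plan specifies, within HIV-status stratum, 150 against 150, two-sided 0.017 and unadjusted, power for OR 1.9 is at most 64.6% against the stated 80%. The chance of missing that effect is at least 35%. The 20%-loss claim for OR 2.1 has at most 67.8%. The stated odds ratio and the stated 17 points are incompatible as absolute figures. The ceilings assume independent participants and no particular control rate. Clustering of referred peers with their nominators is ignored and would usually lower power in Arm 2 comparisons. Why the figures went wrong (unadjusted alpha, or a 2:1 comparison) is inference only.

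**What to change.** Rewrite the power paragraph in 10.2 for the test in 10.3.1:

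- State the assumed control-arm success proportion in each stratum, and how the control-arm benefit mentioned in 3.3.2 enters it.
- Either state 80% power for OR about 2.1 (18 to 19 points) at 150 per arm and about 2.3 (about 21 points) at 120 per arm, if rates centre on 50%, or the equivalents at the named control rate; or keep OR 1.9 and state at most about 65% power, falling to about 53% after 20% loss.
- Remove the pairing of OR 1.9 with 17%. If 17 points was the intended target, give the odds ratio and power that follow from it at the named control rate.
- Optionally, show heavier loss at 12 months, since the endpoint spans the full year: with rates centred on 50%, the 80%-power odds ratio is about 2.46 at 30% loss (105 per arm) and 2.65 at 40% loss (90 per arm).

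The cost is a change of wording in one section and less favourable figures. Recruitment, alpha and analysis stay as they are.
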